7.1 Sample Size Determination

We approximated power and sample size using a simpler model comparing the two groups on change scores in behavioral effects (threat attention bias, reactive aggression) and brain activation (amygdala and striatal response to non-reward) from baseline to addback. With 15 subjects per group, we have 80% power to detect effect sizes of 1.10, which are large and consistent with our previous study (see Preliminary Data). We posit that if treatment with supra physiologic levels of reproductive hormones does not produce large enough differences in neural circuits between HS+ and HS- to be detected in a relatively small sample of women, then this line of research, which involves significant participant burden, is not worth pursuing. Moreover, given the experimental nature of the proposed research, our effect size estimates are more similar to those seen in experimental animal research than in traditional human clinical trials. Nonetheless, our own and other previous clinical research supports our hypothesized large effect. Studies comparing participants with major depression and controls have yielded effect sizes (Cohen's d) ranging from 1.15 to 2.05 in dorsomedial PFC responsivity to negative emotional stimuli (Grimm et al., 2008; Hooley et al., 2005; Moses-Kolko et al., 2010) and from 1.0 to 1.56 in ventral striatum reactivity to reward (Epstein et al., 2006; Moses-Kolko et al., 2011; Moria J Smoski et al., 2009). Studies examining the association between amygdala activation and depressive symptom severity have yielded effect sizes (Cohen's d) ranging from 1.62 to 2.76 (Hamilton & Gotlib, 2008; Moses-Kolko et al., 2010).

Our target number of subjects to include in the fMRI analyses is N=30 (15 confirmed HS+ and 15 confirmed HS-). Because we have not yet identified a mechanism by which we can predict hormone sensitive status at baseline with 100% accuracy, we will need to over-recruit women with a history of PND to account for those who end up not being HS+. In our previous study 11 of the 15 women (73%) with a history of PND were HS+. For the current study, we therefore plan to over-enroll women with a history of PND in order to reach our target of 15 women with confirmed HS+. If 73% of women with a history of PND and no history of non-puerperal major depressive disorder are HS+, then we will need to enroll 21 women to find 15 with confirmed HS+. Based on the 9% dropout rate of our prior trial, we estimated a 9% dropout rate, and as such, we have budgeted for an additional 3 subjects to account for dropouts. In the prior study 2/3 of the women who withdrew from the protocol had a history of PND, so we anticipate 2 women with a history of PND and 1 control (without a history of PND) will withdraw from the proposed study. These numbers are summarized in the following table:

Recruitment Group	Target Enrollment	Confirmed HS+/HS- (included in fMRI/behavioral analysis)	Not HS+/HS- (excluded from fMRI/behavioral analysis)	Withdrawn
History of PND	23	15 HS+	6 not HS+	2
Control (no history of PND)	16	15 HS-	0 not HS-	1
TOTAL	39	30	6	3

Thus, we plan to enroll a total of 39 subjects (n=16 without a history of PND, n=23 with a history of PND).

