Women with a history of PND reported increased irritability, anxiety, dysphoria, and anhedonia during the hormone challenge. Eleven out of 15 (73%) women with a history of PND were HS+ (i.e., showed a 30% increase in IDAS-II affective symptoms during early addback, late addback, or withdrawal compared with baseline). Irritability was the primary symptom for the majority (72%) of HS+, and because irritability distinguished HS+ and HS- as early as 2 weeks into hormone addback ($t=2.97$, $p<.004$; Figure 4), we propose to truncate hormone addback in the current study to 2 weeks (down from 8 weeks in the previous study) and conduct the second fMRI at that time. During the monetary incentive delay (MID) task, there was a significant group x time interaction in the bilateral putamen ($F=5.9$,

$p < .022$), such that HS- showed greater activation than HS+ during hormone withdrawal ($t(26) = 2.8$, $p < .01$) but not at baseline ($t(26) = -0.6$, $p = .54$) (see Figure 5).

[figure not shown]

Figure 4. Irritability self-ratings during each study phase. HS+ ($n=11$) showed significantly increased irritability at early addback, compared with baseline and compared with HS- ($n=14$). The early addback assessment occurred 2 after two weeks of hormone addback (plus Lupron). Symbols:  fMRI session.

[figure not shown]

Figure 5. Percent signal change in bilateral putamen activity during monetary reward at baseline and during hormone withdrawal. Consistent with the literature, as HS+ ($n=11$) became depressed, they showed reduced striatal activation to reward, compared with HS- ($n=14$; non-depressed).

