Sensitivity Analysis. In addition to the statistical tests described below, we will use sensitivity analyses to evaluate the robustness of the study's main results to reasonable perturbations of the statistical methods and assumptions used and to help ensure reproducibility of the main results. Sensitivity analysis will address the inclusion/exclusion of questionable data values (i.e., outliers), the use of alternative methods of coping with missing values and dropouts, and modeling assumptions.

Hypothesis testing. We have detailed both the null and alternative hypotheses we will test below. For all hypothesis tests, we will use the Bonferroni method to correct for multiple comparisons. All hypothesis tests that are observed to be not statistically significant will be reported as being inconclusive. In accordance with the ICMJE and Consort Statement, all statistical estimates of population parameters will be tabulated along with confidence intervals. The interpretation of confidence intervals will be an integral part of the data analysis in concert with the statistical hypothesis tests.

Power calculations overview. We have based our power calculations on previous studies of similar effects (i.e, not pilot studies) with N greater than or equal to 30. Given that prior literature suggests large effect sizes for Aims 1 and 2, we believe that point-estimates will yield relatively accurate power calculations.

Aim 1: To determine the extent to which irritability is characterized by dysfunctional threat processing during reproductive hormone challenge relative to baseline in HS+ and HS-.

Null hypothesis 1: HS+ is not characterized by behavioral activation in the context of potential threat during periods of hormone change in the target population.

Alternative hypothesis 1: HS+ is characterized by behavioral activation in the context of potential threat during periods of hormone change in the target population. Given this hypothesis, we will test the following sub-hypotheses:

Null hypothesis 1a: HS+ is not characterized by threat attention bias during hormone addback relative to baseline in the target population.

Alternative hypothesis 1a: HS+ is characterized by threat attention during hormone addback relative to baseline in the target population.

Independent variables: Group (HS+ versus HS-) and Phase (Visit 3-baseline versus Visit 6-hormone addback)

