Dependent variable: Threat attention bias will be measured using the visual dot probe task at study visits 3 and 6. Threat attention bias will be calculated for the angry-neutral trials by subtracting the mean reaction time (measured in milliseconds) on trials where the asterisk

appears on the same side as the angry face from the mean reaction time on trials where the asterisk appears on the same side as the neutral face.

Analysis: 2x2 Repeated Measures ANOVA will be used to analyze the effects of Group (HS- vs. HS+) and Phase (baseline vs. hormone addback) on threat attention bias.

Power: We used G*Power 3.1 for Mac to calculate power. We anticipate an effect size $f=0.3$ based on a previous study of threat attention bias in those with and without mood dysregulation (Hommer et al., 2014). If we set $\alpha=.05$, we will have 87% power to reject the null hypothesis with a total sample size of $N=30$.

Null hypothesis 1b: HS+ is not characterized by reduced amygdala-medial PFC connectivity in response to threatening stimuli during hormone addback relative to baseline in the target population.

Alternative hypothesis 1b: HS+ is characterized by reduced amygdala-medial PFC connectivity in response to threatening stimuli during hormone addback relative to baseline in the target population.

Independent variables: Group (HS+ versus HS-) and Phase (Visit 3-baseline versus Visit 6-hormone addback)

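### The power figures in 7.1 and 7.2 disagree with each other, and the previous study's change effect (d about 0.95) gives about 71% power with 15 per group

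*Combined protocol and SAP*

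**What the plan says.** Section 7.1 describes its method: "We approximated power and sample size using a simpler model comparing the two groups on change scores in behavioral effects" and in brain activation, from baseline to addback. It continues: "With 15 subjects per group, we have 80% power to detect effect sizes of 1.10, which are large and consistent with our previous study". Appendix C (III.A) repeats the 1.10 without the 80%, and its statistical strategy (V.A) names the group-by-time interaction as the effect of principal interest.

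The imaging results from the previous study are in section 1.4. On a monetary reward task "there was a significant group x time interaction in the bilateral putamen" (F = 5.9), "such that HS- showed greater activation than HS+ during hormone withdrawal" (t(26) = 2.8), with no baseline difference (t(26) = -0.6).

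Section 7.2 gives separate power statements, all at alpha .05 and N = 30:
- Hypothesis 1a: "We anticipate an effect size $f=0.3$ based on a previous study of threat attention bias in those with and without mood dysregulation", with 87% power for a 2x2 repeated-measures ANOVA.
- Hypothesis 2a: d = .95 from a testosterone-versus-placebo study becomes f = .45, with power above 99%.

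Section 7.2 also promises a Bonferroni correction for all tests. On a null result, 7.1 says that if the differences in neural circuits are too small to detect in this sample, "then this line of research, which involves significant participant burden, is not worth pursuing". Section 7.2 says: "All hypothesis tests that are observed to be not statistically significant will be reported as being inconclusive".

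**The concern.** In a 2x2 design with two visits, the interaction is the group difference in change. A power figure for that test needs an effect on the change-score scale. A group difference at one visit is on another scale, and the two are linked only through the correlation between visits and any baseline difference.

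Section 7.1 appeals to the previous study for 1.10, but that study's reported change effect is smaller. Section 7.2 gives no visit correlation and no G*Power option, and its figures imply change effects well above the one 7.1 calls large. A reader cannot tell what the trial is able to detect. This matters more because 7.1 draws a conclusion about the whole research line from failure to detect a neural difference.

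**Working it through.** **Inputs.** 15 per group, d = 1.10 and 80% (7.1). F = 5.9, t(26) = 2.8, and captions with 11 HS+ and 14 HS- (1.4). f = 0.3 with 87%, and d = .95 with f = .45 and over 99% (7.2). The visit correlation rho is not stated, so it is varied.

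**1. The plan's 7.1 figure.** Two-sample t test on change, two-sided .05, 28 df, noncentrality d x sqrt(15/2). At d = 1.10 power is 82.8%. Power of 80% is reached at d = 1.06. The stated 80% is slightly conservative.

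**2. The previous study's change effect.** With two groups and two visits, t = sqrt(5.9) = 2.429.

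| Conversion | d | Power, 15 per group |
|---|---|---|
| 2t/sqrt(26) | 0.953 | 71.2% |
| t x sqrt(2/14), 14 and 14 | 0.918 | 68.0% |
| t x sqrt(1/11 + 1/14) | 0.979 | 73.5% |

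The spread arises because 26 df implies 28 women, while the captions give 25.

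**3. Hypothesis 1a.** G*Power's within-between interaction option uses lambda = f² x N x m/(1 - rho), with m = 2 visits and F on 1 and 28 df.
- At rho = .5, lambda = 0.09 x 30 x 2/0.5 = 10.8 and power is 88.7%. At rho = .47 it is 86.9%, the stated 87%.
- The between-groups option gives 44.9% at rho = .5 and does not reproduce 87%.
- The change-score test has lambda = 7.5d², so 10.8 implies d = sqrt(10.8/7.5) = 1.20, above 7.1's 1.10.

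With two groups f = d/2, so f = 0.3 may instead mean a gap of 0.6 SD between groups. If that gap is absent at baseline and present at addback, the change-score d is 0.6/sqrt(2(1 - rho)):

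| rho | change d | power |
|---|---|---|
| 0 | 0.42 | 20% |
| .3 | 0.51 | 27% |
| .5 | 0.60 | 35% |
| .7 | 0.77 | 54% |

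**4. Hypothesis 2a.** The plan's step from .95 to .45 is close to d/2 = .475, the two-group conversion. In the interaction option at rho = .5, lambda = 0.2025 x 60/0.5 = 24.3 and power is 99.7%, as stated. The implied change-score d is sqrt(24.3/7.5) = 1.80, about twice the cited .95. Under 7.1's model, a change-score d of .95 gives 71%. If .95 is a gap at addback only, the same formula gives d = 0.67 at rho = 0 and 1.23 at rho = .7, with power of 43% and 90%.

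**5. Bonferroni.** The plan does not say how many tests share alpha. Assuming four (1a, 1b, 2a, 2b), alpha is .05/4 = .0125. Power is then 64% at d = 1.10, 49% at 0.953 and 17% at 0.6.

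**6. What a null would show.** At alpha .05, an observed d below 2.048 x sqrt(2/15) = 0.75 is non-significant. The 95% interval still includes 1.10 whenever the observed d is above about 0.38. Any result between 0.38 and 0.75 is therefore non-significant and still compatible with the effect the trial was sized for.

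**The case against.** The strongest reply is that 7.1 states power for a named effect and the arithmetic is sound. Putting in 0.95 changes the assumption and corrects no error. That stands, and a reader who infers that the 80% should have been 71% goes too far.

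The interaction estimate is also imprecise. Its 95% interval runs from roughly 0.13 to between 1.7 and 1.8, so 1.10 is not ruled out. It comes from a different task, at withdrawal from a longer and higher-dose regimen. Section 7.1 cites other literature effects too, from 1.0 to 2.76. All this limits 0.95 as a forecast, but it limits the appeal to the previous study in the same way.

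A reader might infer that 1.10 was taken from the single-visit contrast, since 2 x 2.8/sqrt(26) = 1.098. The documents do not say so. Other conversions of the same t give 1.06 or 1.13, and the irritability result at two weeks of addback (t = 2.97) gives about 1.12 to 1.20. The match is suggestive only.

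For 1a, the source of f = 0.3 is described in one phrase. If it is a true interaction effect, the 87% stands. The 35% needs f = 0.3 to be a two-group gap, no baseline difference and rho = .5.

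The sentence in 7.1 about the research line is design rationale on neural differences. It does not cover 1a, a reaction-time task, so the 65% chance of a null there cannot be set against it. Section 7.2 already asks for interpretation of confidence intervals.

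**Conclusion.** The concern holds as a matter of support and consistency. On the change scale that the test uses, the previous study's imaging effect is about 0.95, for which 15 per group has about 71% power (68% to 74%) at unadjusted alpha. That leaves about a 29% chance of a null on a single test if the effect is real.

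Sections 7.1 and 7.2 cannot both describe the same test on the same scale. The first gives 80% for 1.10, while the second gives over 99% starting from a cited .95, and its 87% for 1a needs about 1.2. The treatment of 2a makes it plausible that two-group effects were entered as interaction effects, but the plan does not give the settings that would confirm it. The 35% for 1a is therefore conditional, with a range of 20% to 54%.

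A reader might extend the point to every power figure. The documents do not support that: the effects cited for 1b and 2b are described as changes with treatment. The missing Bonferroni adjustment does apply to all the figures.

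**What to change.** Change the wording in 7.1, 7.2 and Appendix C; N stays the same.

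- **7.1 and Appendix C:** state that 15 per group gives 80% power for a change-score d of 1.06, and about 71% for the previous study's group-by-time effect of about 0.95.
- **Hypotheses 1a and 2a:** state the effect on the change-score scale with its source, the assumed visit correlation and the G*Power option. Replace 87% and the figure above 99% with the resulting power. If the cited effects are two-group differences (d = 2f), that is about 35% for 1a and about 71% for 2a at rho = .5, each with its range over rho.
- **All power statements:** name the number of tests that share alpha and add power at the Bonferroni level.
- **Null results:** say that a null on the neural endpoints argues against the research line only if the confidence interval for the standardized difference in change excludes 1.10. Otherwise it is inconclusive, as 7.2 already says.

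The cost is an edit to the text and less favourable stated power. No procedure or visit changes.

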7.2 Statistical Methods

We have defined HS+ as a 30% or greater change in any of the IDAS-II mood scales, which include dysphoria, suicidality, ill temper (i.e., irritability), and wellbeing (i.e., reverse-keyed) during hormone addback or withdrawal, compared with the individual's own baseline using the equation below:

$$\% \text{ symptom change} = (\text{Addback score} - \text{Baseline score}) / \text{Baseline score}$$

Percent symptom change will be calculated for each of the IDAS-II scales listed above at both the addback visit (V6) and withdrawal visit (V7). If a participant has a percent symptoms change of 30% or greater on any of the IDAS-II scales listed, she will be classified as HS+. HS- is defined as less than 30% change in any of the IDAS-II mood scales.

We will only include those with confirmed HS+ and HS- in our planned analyses. Those with a history of PND confirmed to be HS- will be excluded from planned analyses. However, if we have enough subjects with a history of PND who are HS-, then they may be included as a separate group in exploratory analyses. Alternatively, if those with a history of PND who are HS- are not significantly different from those without a history of PND who are HS- in terms of our key outcome variables, then we will pool the groups to increase power.

The IDAS-II is scored using a 5-point Likert scale, ranging from 1 "Not at all" to 5 "Extremely." The scales we will use to determine hormone sensitivity and their ranges are listed in the table below:

IDAS-II Scale	Minimum Score	Maximum Score
Dysphoria	10	50
Suicidality	6	30
Ill Temper	5	25
Wellbeing	8	40

Missingness. We will use multiple imputation to correct for data determined to be missing at random, given that it is a reliable method for obtaining valid inferences in both behavioral and fMRI research (Rubin, 1987; Vaden et al., 2012). Data for dropouts will be compared with data for those who complete

the study to determine the extent to which excluding their data will introduce selection bias, and selection bias will be identified as a weakness in any resulting publications or presentations.

Sensitivity Analysis. In addition to the statistical tests described below, we will use sensitivity analyses to evaluate the robustness of the study's main results to reasonable perturbations of the statistical methods and assumptions used and to help ensure reproducibility of the main results. Sensitivity analysis will address the inclusion/exclusion of questionable data values (i.e., outliers), the use of alternative methods of coping with missing values and dropouts, and modeling assumptions.

Hypothesis testing. We have detailed both the null and alternative hypotheses we will test below. For all hypothesis tests, we will use the Bonferroni method to correct for multiple comparisons. All hypothesis tests that are observed to be not statistically significant will be reported as being inconclusive. In accordance with the ICMJE and Consort Statement, all statistical estimates of population parameters will be tabulated along with confidence intervals. The interpretation of confidence intervals will be an integral part of the data analysis in concert with the statistical hypothesis tests.

Power calculations overview. We have based our power calculations on previous studies of similar effects (i.e, not pilot studies) with N greater than or equal to 30. Given that prior literature suggests large effect sizes for Aims 1 and 2, we believe that point-estimates will yield relatively accurate power calculations.

Aim 1: To determine the extent to which irritability is characterized by dysfunctional threat processing during reproductive hormone challenge relative to baseline in HS+ and HS-.

Null hypothesis 1: HS+ is not characterized by behavioral activation in the context of potential threat during periods of hormone change in the target population.

Alternative hypothesis 1: HS+ is characterized by behavioral activation in the context of potential threat during periods of hormone change in the target population. Given this hypothesis, we will test the following sub-hypotheses:

Null hypothesis 1a: HS+ is not characterized by threat attention bias during hormone addback relative to baseline in the target population.

Alternative hypothesis 1a: HS+ is characterized by threat attention during hormone addback relative to baseline in the target population.

Independent variables: Group (HS+ versus HS-) and Phase (Visit 3-baseline versus Visit 6-hormone addback)

Dependent variable: Threat attention bias will be measured using the visual dot probe task at study visits 3 and 6. Threat attention bias will be calculated for the angry-neutral trials by subtracting the mean reaction time (measured in milliseconds) on trials where the asterisk

appears on the same side as the angry face from the mean reaction time on trials where the asterisk appears on the same side as the neutral face.

Analysis: 2x2 Repeated Measures ANOVA will be used to analyze the effects of Group (HS- vs. HS+) and Phase (baseline vs. hormone addback) on threat attention bias.

Power: We used G*Power 3.1 for Mac to calculate power. We anticipate an effect size $f=0.3$ based on a previous study of threat attention bias in those with and without mood dysregulation (Hommer et al., 2014). If we set $\alpha=.05$, we will have 87% power to reject the null hypothesis with a total sample size of $N=30$.

Null hypothesis 1b: HS+ is not characterized by reduced amygdala-medial PFC connectivity in response to threatening stimuli during hormone addback relative to baseline in the target population.

Alternative hypothesis 1b: HS+ is characterized by reduced amygdala-medial PFC connectivity in response to threatening stimuli during hormone addback relative to baseline in the target population.

Independent variables: Group (HS+ versus HS-) and Phase (Visit 3-baseline versus Visit 6-hormone addback)

Dependent variable: Amygdala-medial PFC connectivity will be assessed during the implicit face emotion processing fMRI task at study visits 3 and 6. Functional connectivity expresses the statistical dependency among activations in different brain regions and results in undirected (symmetrical) connectivity matrices and will be calculated according to standard procedures (Walsh et al., 2017). We will use a generalized psychophysiological interaction (gPPI) approach for detecting context-dependent functional connectivity (Cisler et al., 2014; McLaren et al., 2012). Replicating the methods of Walsh et al. (2017), we will use an ROI approach to target the amygdala, which will be defined using the Harvard-Oxford subcortical atlas. Voxel-wise models will be used to evaluate connectivity with the amygdala seed. For each participant, mean fMRI time courses will be extracted from the amygdala seed using the “fslmeans” program in FSL, then multiplied by each psychological regressor of interest (i.e., task condition) to form the PPI interaction terms. The gPPI model will include physiological and psychological regressors, as well as their interaction terms to describe the unique effect of these interactions above and beyond the main effects of seed time courses and task conditions. Our primary contrast of interest will evaluate the difference between connectivity during presentation of threatening stimuli versus non-threatening stimuli. This allows for the characterization of connectivity patterns specific to threat processing.

Analysis: Group and phase differences will be evaluated with respect to seed-based connectivity specific to threat processing using a 2x2 mixed effects analysis with Bayesian estimation techniques with FMRIB Local Analysis of Mixed Effects (Smith et al., 2004).

Clusters will be thresholded at $Z>2.58$ or $p<.005$ corrected with a minimum contiguous cluster size of 8 (Walsh et al., 2017).

Power: We used G*Power 3.1 for Mac to calculate power. While few studies have examined changes in amygdala-PFC between those with and without depression following treatment, the few extant studies yielded large effects ($d=1.3$) (Straub et al., 2017). If we anticipate an effect size $f=.5$ and set $\alpha=.05$, we will have greater than 99% power to reject the null hypothesis with a total sample size of $N=30$.

Null hypothesis 1c (secondary): In HS+, the degree of irritability, threat attention bias, and amygdala-medial PFC connectivity during hormone addback are unrelated in the target population.

Alternative hypothesis 1c (secondary): In HS+, irritability is associated with 1) threat attention bias, and 2) amygdala-medial PFC connectivity during hormone addback in the target population.

“Independent” variable: Irritability will be defined as scores on the IDAS-II ill temper scale at study visit 6.

“Dependent” variables: Threat attention bias at study visit 6 will be calculated in the same way as for hypothesis 1a. Amygdala-medial PFC connectivity at study visit 6 will be calculated in the same way as for hypothesis 1b.

Analysis: Pearson’s r will be calculated for correlations between irritability and 1) threat attention bias and 2) amygdala medial-PFC connectivity during hormone addback (study visit 6) in HS+.

Power: We have not powered to the study to assess secondary hypotheses. We used G*Power 3.1 for Mac to calculate power. Prior research suggests the association between irritability and threat attention bias has a medium effect size (Spearman’s $\rho=.3$) (Hommer et al., 2014). If we anticipate an effect size $\rho=.3$ and set $\alpha=.05$ (two-tailed), we will have less than 20% power to reject the null hypothesis with a HS+ sample size of $n=15$. There is not enough information to predict the strength of the association between irritability and amygdala medial-PFC connectivity.

Aim 2: To determine the extent to which irritability is characterized by dysfunctional reward processing during reproductive hormone challenge relative to baseline in HS+ and HS-.

Null hypothesis 2: HS+ is not characterized by increased frustration in the context of non-reward (i.e., when reward is expected) during hormone addback relative to baseline in the target population.

Alternative hypothesis 2: HS+ is characterized by increased frustration in the context of non-reward during hormone addback relative to baseline in the target population. Given this hypothesis, we will test the following sub-hypotheses:

Null hypothesis 2a: HS+ is not characterized by reactive aggression during hormone addback relative to baseline in the target population.

Alternative hypothesis 2a: HS+ is characterized by reactive aggression during hormone addback relative to baseline in the target population.

Independent variables: Group (HS+ versus HS-) and Phase (Visit 3-baseline versus Visit 6-hormone addback)

Dependent variable: Reactive aggression will be defined as the number of point subtractions the participant makes during the Point Subtraction Aggression Paradigm.

Analysis: 2x2 Repeated Measures ANOVA will be used to analyze the effects of Group (HS- vs. HS+) and Phase (baseline vs. hormone addback) on threat attention bias.

Power: We used G*Power 3.1 for Mac to calculate power. We anticipate a large effect size based on a previous study examining reactive aggression using the Point Subtraction Aggression Paradigm in men who were treated with testosterone versus placebo ($d=.95$) . If we estimate the effect size $f=.45$ and set $\alpha=.05$, we will have greater than 99% power to reject the null hypothesis with a total sample size of N=30.

Null hypothesis 2b: HS+ is not characterized by reduced activation of the amygdala and ventral striatum in response to FNR during hormone addback relative to baseline in the target population.

Alternative hypothesis 2b: HS+ is characterized by reduced activation of the amygdala and ventral striatum in response to FNR during hormone addback relative to baseline in the target population.

Independent variables: Group (HS+ versus HS-) and Phase (Visit 3-baseline versus Visit 6-hormone addback)

Dependent variable: Activation in amygdala and ventral striatum (caudate, putamen, nucleus accumbens) ROIs during the Affective Posner Task. Event types include three categories: trial type (money, no money), validity (valid, invalid), and feedback (positive, negative, error). Combination of these three factors will be modeled using individual linear regression with a fixed-shape, gamma-variate response function, convolved with a boxcar function of the stimulus duration. FNR will be defined as the contrast between positive valid money trials and negative valid money trials (i.e., the difference between expecting money and getting it and expecting money and not getting it).

Analysis: The model will include each of the two event-type regressors (to model FNR), the six motion parameters, and baseline drift for each of the runs. Beta coefficients and t-statistics will be calculated for each voxel and regressor. Group level analyses will be conducted on the amygdala and striatum (caudate, putamen, and nucleus accumbens), as defined by the Harvard-Oxford subcortical atlas. Mean signal intensity will be extracted from each ROI for each of the event types using FSL. Signal intensity values will be submitted to a Group x Trial type x Feedback x Phase x Region ANCOVA in SPSS.

Power: We used G*Power 3.1 for Mac to calculate power. We anticipate a large effect size based on previous studies examining changes in amygdala activation with various treatments ($d=1.58$ to 1.96) (Hauner et al., 2012; Riem et al., 2011). If we estimate the effect size $f=.5$ and set $\alpha=.05$, we will have greater than 99% power to reject the null hypothesis with a total sample size of $N=30$.

Null hypothesis 2c (secondary): The degree of irritability, reactive aggression, and subcortical (amygdala, caudate, putamen, and nucleus accumbens) activation in HS+ during hormone addback are unrelated in the target population.

Alternative hypothesis 2c (secondary): In HS+, self-reported irritability is associated with 1) reactive aggression, and 2) subcortical (amygdala, caudate, putamen, and nucleus accumbens) activation during hormone addback in the target population.

“Independent” variable: Irritability will be defined as scores on the IDAS-II ill temper scale at study visit 6.

“Dependent” variables: Reactive aggression at study visit 6 will be calculated in the same way as for hypothesis 2a. Subcortical activation at study visit 6 will be calculated in the same way as for hypothesis 2b.

Analysis: Pearson’s r will be calculated for correlations between irritability and 1) reactive aggression and 2) subcortical activation during hormone addback (study visit 6) in HS+.

Power: We have not powered to the study to assess secondary hypotheses. We used G*Power 3.1 for Mac to calculate power. Prior research suggests the association between irritability and reactive aggression has a large effect size (Pearson’s $r=.6$) in a civilian population (Geniole et al., 2017). If we anticipate an effect size $r=.3$ and set $\alpha=.05$ (two-tailed), we will have 70% power to reject the null hypothesis with a HS+ sample size of $n=15$. There is not enough information to predict the strength of the association between irritability and subcortical activation in response to FNR.

